5.2.2 Secondary Endpoints

Immunogenicity:

- GMTs of neutralizing antibodies (MNT₅₀) for each of the 4 dengue serotypes at 6 months post second dose (Day 270 [M9]).
- Seropositivity rates (% of subjects seropositive) for each of the 4 dengue serotypes at 1 month and 6 months post second dose (Day 120 [M4]) and Day 270 [M9], respectively).
- Seropositivity rates (% of subjects seropositive) for multiple (2, 3, or 4) dengue serotypes at 1 month and 6 months post second dose (Day 120 [M4]) and Day 270 [M9], respectively).

Note: Seropositivity is defined as a reciprocal neutralizing titer ≥ 10 .

Safety:

- Frequency and severity of solicited local (injection site) adverse events (AE) for 7 days (day of vaccination+6 subsequent days) and solicited systemic AEs for 14 days (day of vaccination+13 subsequent days) after each TDV/placebo dose on Day 1 (M0) and Day 90 (M3).
- Percentage of subjects with any unsolicited AEs for 28 days (day of vaccination+27 subsequent days) after each TDV/placebo dose on Day 1 (M0) and Day 90 (M3).
- Percentage of subjects with medically attended AEs (MAAE) and serious adverse events (SAE) throughout the trial.

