10.1.2 Solicited Adverse Events

The occurrence of selected indicators of safety as listed in [Table 10.a](#) will be measured/collected for 7 days (solicited local [injection site] AEs) and 14 days (solicited systemic AEs) following administration of each trial vaccine dose (including the day of administration) and will be recorded on the “Local and Systemic AEs” eCRF, as applicable. These will be summarized in the final report under the category “solicited AEs” to differentiate them from other AEs which were not solicited. Any solicited local or systemic AE observed as continuing 8 days and 15 days, respectively, following each trial vaccination will be recorded as an unsolicited AE on the “AE” eCRF.

Table 10.a Solicited Local and Systemic Adverse Events

Solicited local (injection site) AEs:	Pain Erythema Swelling
Solicited systemic AEs:	Fever ^(a) Headache Asthenia Malaise Myalgia

(a) Fever is defined as greater than or equal to 38°C (100.4°F) regardless of method taken [[15](#)].

The severity of solicited safety parameters will be assessed as described in [Table 10.b](#).

Table 10.b Severity Scales for Solicited Safety Parameters

Adverse Event	Severity grade	Severity
Pain at injection site	0	None
	1	Mild: No interference with daily activity
	2	Moderate: Interference with daily activity with or without treatment
	3	Severe: Prevents daily activity with or without treatment
Erythema at injection site ^(a)	0	<25 mm
	1	Mild: $\geq 25 - \leq 50$ mm
	2	Moderate: $>50 - \leq 100$ mm
	3	Severe: >100 mm
Swelling at injection site ^(a)	0	<25 mm
	1	Mild: $\geq 25 - \leq 50$ mm
	2	Moderate: $>50 - \leq 100$ mm
	3	Severe: >100 mm
Headache	0	None
	1	Mild: No interference with daily activity
	2	Moderate: Interference with daily activity with or without treatment
	3	Severe: Prevents normal activity with or without treatment
Asthenia	0	None
	1	Mild: No interference with daily activity
	2	Moderate: Interference with daily activity
	3	Severe: Prevents daily activity
Malaise	0	None
	1	Mild: No interference with daily activity
	2	Moderate: Interference with daily activity
	3	Severe: Prevents daily activity
Myalgia	0	None
	1	Mild: No interference with daily activity
	2	Moderate: Interference with daily activity
	3	Severe: Prevents daily activity
Fever ^(b)	Record body temperature in °C/°F	

(a) Subjects are to record greatest surface diameter in mm on the diary card.

(b) Fever is defined as greater than or equal to 38°C (100.4°F) regardless of method taken [15].

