10.4.2 Collection and Reporting of Solicited Adverse Events

The occurrence of selected indicators of safety will be collected on diary cards by the subject/LAR for 7 days (solicited local [injection site] AEs) and 14 days (solicited systemic AEs) following administration of each trial vaccine dose (including the day of administration) and will be recorded on the “Local and Systemic AEs” eCRF, as appropriate. Any solicited local (injection site) or systemic AE observed as continuing 8 days and 15 days, respectively, following each trial dose administration, will be recorded as an unsolicited AE on the AE eCRF. Any solicited local (injection site) or systemic AE that resolved before 8 days and 15 days, respectively, following each trial dose administration, but which recurs at a later time (ie, if discontinues), will be recorded as an unsolicited AE on the AE eCRF.

Any solicited AE that meets any of the following criteria must be entered as an AE on the AE eCRF:

- Solicited local (injection site) or systemic AEs that lead the subject to withdraw from the trial.
- Solicited local (injection site) or systemic AEs that lead to the subject being withdrawn from the trial by the Investigator.
- Solicited local (injection site) and systemic AEs that otherwise meet the definition of an SAE (see Section 10.1.2).

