- Days 1 – 3 and Days 4 – 7 (solicited local [injection site] AEs)
- Days 1 – 7 and Days 8 – 14 (solicited systemic AEs)

For subjects with more than 1 episode of the same event, the maximum severity will be used for tabulations.

For solicited systemic AEs, the number and percentage of subjects will also be summarized by relationship to IP (assessed by the Investigator) for the following intervals post-vaccination:

- 30 minutes
- Within 14 days

Subjects will only be counted once if the subject has more than 1 episode of the same event. In the case where the subject has both related and unrelated solicited systemic AEs, the subject will be counted under the related category. All solicited local (injection site) AEs are considered as related to IP.

A summary of the day of first onset of each event and the number of days subjects reported each event will be presented post-vaccination. The number of days a subject reported each event is calculated as the total of all days the subject reported the event, regardless of whether the event was reported on consecutive days.

An overview table for solicited AEs post-vaccination will be provided including:

- 30 minutes in-clinic assessment (solicited local [injection site] and systemic AEs combined)
- Solicited AEs (solicited local [injection site] and systemic AEs combined)
- Solicited local [injection site] AEs
- Solicited systemic AEs (overall and by relationship to IP)
- Prolonged solicited AEs (overall and for solicited local [injection site] and systemic AEs separately)

Prolonged solicited AEs that continue beyond Day 7 (for local [injection site] AEs) or Day 14 (for systemic AEs) will be captured on the AE CRF with appropriate indication (“continued solicited AE”). These prolonged solicited AEs will be presented in separate listings and will not be included in any unsolicited AE summary or listing.

Unsolicited AEs

Unsolicited AEs will be assessed for 28 days following administration of each trial dose (day of vaccination + 27 subsequent days). MAAEs, SAEs and AEs leading to IP withdrawal or trial discontinuation will be collected from first trial dose (Day 1 [M0]) until the end of the trial (Day 270 [M9]). Unsolicited AEs, MAAEs, SAEs, and AEs leading to IP withdrawal or trial discontinuation will be coded according to the current version of MedDRA and summarized by SOC and PT.

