In general, the number of events, number of subjects, and the percentage of subjects will be tabulated by trial group at each of the following levels: overall summary (any AEs/subjects with any AEs) and by SOC and PT. Subjects reporting more than 1 occurrence for the term (level) being summarized will be counted only once in the number/percentage of subjects. Percentages will be based on the number of subjects in the Safety Set who received the respective trial dose.

Unsolicited AEs up to 28 days post-vaccination will be summarized as follows:

- By SOC and PT;
- By SOC and PT including events with frequency greater than 2% in any trial group;
- By SOC and PT including non-serious events with frequency greater than 2% in any trial group (including a separate group of subjects who received different IPs at first and second vaccination [if any]);
- By SOC and PT for IP related events;
- By SOC and PT for IP related events with frequency greater than 2% in any trial group;
- By SOC, PT, and severity (mild, moderate, severe).

MAAEs post-vaccination throughout the trial duration will be summarized as follows:

- By SOC and PT;
- By SOC and PT for IP related events;
- By SOC, PT, and severity (mild, moderate, severe).

SAEs post-vaccination throughout the trial duration will be summarized as follows:

- By SOC and PT (including a separate group of subjects who received different IPs at first and second vaccination [if any]);
- By SOC and PT for IP related events.

AEs leading to IP withdrawal or trial discontinuation post-vaccination throughout the trial duration will be summarized as follows:

- By SOC and PT (including a separate group of subjects who received different IPs at first and second vaccination [if any]);

- By SOC and PT for IP related events.

In addition, overview tables by trial group will be generated for unsolicited AEs (collected up to 28 days post-vaccination), SAEs, MAAEs and AEs leading to IP withdrawal or trial discontinuation including the variables as outlined in [Table 7.d](#).

Table 7.d Overview of Unsolicited Adverse Events

	All AEs (28 days post- vaccination)	SAEs	MAAEs	AEs leading to IP withdrawal and/or trial discontinuation
Relationship to IP	✓	✓	✓	✓
Relationship to trial procedure	✓	✓	✓	✓
Severity	✓	✓	✓	✓
AEs leading to IP withdrawal and/or trial discontinuation	✓	✓	✓	
AEs leading to IP withdrawal	✓	✓	✓	✓
AEs leading to trial discontinuation	✓	✓	✓	✓
MAAEs	✓			✓
SAEs and Non-serious AEs	✓			✓
Deaths	✓	✓		✓

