7.13 Changes in the Statistical Analysis Plan

The SAP contains no changes to the planned analyses described in the protocol.

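### SAP 7.11.1 keeps prolonged solicited AEs out of the unsolicited AE summaries, although the protocol classes them as unsolicited; the change is undeclared, and its reach to SAE, MAAE and discontinuation tables is unclear

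*SAP*

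**What the plan says.** **Protocol.** Section 10.1.2 says that a local or systemic solicited AE "observed as continuing 8 days and 15 days, respectively, following each trial vaccination will be recorded as an unsolicited AE" on the AE eCRF. Section 10.4.2 repeats this. It treats a solicited AE that resolves inside the window in the same way, "but which recurs at a later time (ie, if discontinues), will be recorded as an unsolicited AE on the AE eCRF". It also requires entry on the AE eCRF for solicited AEs that lead to withdrawal and for "Solicited local (injection site) and systemic AEs that otherwise meet the definition of an SAE". Section 10.4.3 requires every MAAE to be entered there, with no exception for events that began as solicited.

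One secondary safety endpoint in section 5.2.2 is the "Percentage of subjects with any unsolicited AEs for 28 days (day of vaccination+27 subsequent days) after each TDV/placebo dose". Another is the percentage of subjects with MAAEs and SAEs over the whole trial.

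**SAP.** Section 7.11.1 captures solicited AEs that run past Day 7 (local) or Day 14 (systemic) on the AE CRF, with a flag marking them as continued. It then says: "These prolonged solicited AEs will be presented in separate listings and will not be included in any unsolicited AE summary or listing". The overview table for solicited AEs keeps a row for prolonged events, in total and split into local and systemic.

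The summaries of SAEs, MAAEs and AEs leading to withdrawal or discontinuation follow under the SAP's unsolicited AE heading. Their overview columns are in Table 7.d, titled "Overview of Unsolicited Adverse Events". Section 7.13 states: "The SAP contains no changes to the planned analyses described in the protocol".

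**The concern.** The two documents put the same event in different categories, and a secondary endpoint is a count of subjects in one of those categories. The SAP's rule therefore computes that endpoint on a different set of events from the one the protocol's classification gives, while stating that nothing has changed. A reader of the study report would have no notice of the difference.

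The second issue is what a programmer would do with the word *any* in the exclusion. If records carrying the continued flag are dropped from everything under the unsolicited AE heading, a prolonged reaction that was serious, led to a medical visit or ended participation would also leave the SAE, MAAE or discontinuation tables. The endpoint on MAAEs and SAEs would then depend on how one sentence was read.

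**Working it through.** The documents state no rate for prolonged solicited AEs and no sample-size calculation, so there is no plan figure to reproduce. The check is mainly a comparison of text, with arithmetic for scale.

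**1. Is the event inside the endpoint window?** The unsolicited window is the day of vaccination plus 27 days, that is Days 1 to 28. A local event becomes unsolicited at Day 8 and a systemic event at Day 15. Both lie within 28 days, and so does the original onset.

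**2. Direction of the difference.** For one dose period, let U be the subjects with another unsolicited AE, F those with a prolonged solicited AE, and N the subjects dosed.
- SAP percentage: |U| / N.
- Percentage under the protocol's classification: |U or F| / N.
- Gap: |F and not U| / N, which is never negative.

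The gap is the share of subjects whose only unsolicited AE is a prolonged solicited AE.

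**3. Size, under assumptions.** Write u = |U|/N and f = |F|/N. Neither is in the documents; I assume u of 10 to 40% and f of 0 to 5%. Group sizes are the planned 300 TDV and 100 placebo, all assumed dosed.
- Full overlap: gap = max(u, f) − u = 0, since f is below u throughout.
- Independence: gap = f(1 − u).
- No overlap: gap = f.

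| f | Gap if independent, u = 10% / 20% / 40% (points) | Gap with no overlap (points) | Most subjects affected, TDV / placebo |
|---|---|---|---|
| 0% | 0 / 0 / 0 | 0 | 0 / 0 |
| 1% | 0.9 / 0.8 / 0.6 | 1 | 3 / 1 |
| 3% | 2.7 / 2.4 / 1.8 | 3 | 9 / 3 |
| 5% | 4.5 / 4.0 / 3.0 | 5 | 15 / 5 |

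For example, f = 5% and u = 10% give 0.05 × 0.90 = 4.5 points.

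**4. Frequency-limited tables.** SAP 7.11.1 has tables restricted to terms above 2% in any group. The smallest qualifying count is 7 of 300 TDV subjects (2.3%; 6 of 300 is exactly 2.0%) or 3 of 100 placebo subjects (2 of 100 is exactly 2.0%). A few reclassified events could decide whether a preferred term appears.

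**5. Does the exclusion reach SAEs, MAAEs and discontinuations?**
- Pointing to yes: the SAP's heading, the title of Table 7.d, and protocol 6.2 and 9.1.7, which both describe unsolicited AEs as comprising non-serious AEs and SAEs.
- Pointing to no: SAP 7.11.1 names unsolicited AEs, SAEs, MAAEs and discontinuation AEs as separate items when it describes coding, overview tables and subject mappings. The endpoint on MAAEs and SAEs carries no solicited or unsolicited qualifier.

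No sentence in the SAP settles it.

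**6. Continuing versus recurring events.** The protocol makes both unsolicited. The SAP's exclusion names only those that continue. As written, a reaction that stops and returns can count as unsolicited, while one that never stops does not.

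**The case against.** **The protocol sentences govern where an event is recorded, not how it is tabulated.** Protocol 13.1.4 does not say how continued solicited AEs are summarized. This has some force. However, the rule in 10.1.2 directly follows a sentence on how the final report will categorize events, and 13.1.4 summarizes unsolicited AEs without any exception.

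**Excluding the events avoids showing one episode under two headings.** This stands as a defensible analytic choice. It is why a declared exclusion from the 28-day tables is acceptable. It does not excuse leaving the change undeclared.

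**Nothing is lost.** This also stands. A prolonged event begins inside the diary window and is counted there by severity and day. It also appears in the prolonged-event row and in listings, and the AE eCRF records its seriousness, severity, causality, action taken and outcome. A reader might infer missing safety data, and the documents do not support that. What is absent is a by-group tabulation: the overview row shows neither seriousness, medical attendance nor withdrawal.

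**The SAE and MAAE tables are separate from unsolicited AE summaries.** A reader might infer that serious or medically attended prolonged events necessarily drop out. The separate naming in SAP 7.11.1 does not support that as the literal reading. What remains is an ambiguity with textual support on both sides.

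**The trial is descriptive.** No hypothesis test or primary endpoint depends on this, which limits the severity.

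**Conclusion.** The conflict is real and undeclared: protocol 10.1.2 and 10.4.2 on one side, SAP 7.11.1 on the other, with SAP 7.13 denying any change. For the 28-day endpoint the SAP's percentage is equal to or lower than the one under the protocol's classification. The difference is 0 to 5 points if 0 to 5% of subjects have a prolonged solicited AE, which is at most 15 of 300 TDV and 5 of 100 placebo subjects. That range is an assumption. The difference is zero if no event is prolonged or if every affected subject has another unsolicited AE.

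A reader might infer that the endpoint is certainly understated, or that the shortfall falls mainly on TDV because the placebo is saline. Neither document gives a rate by group, so a larger effect in TDV is a plausible expectation and nothing more.

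For SAEs, MAAEs and discontinuations, the finding is an unresolved ambiguity. Overall this should be fixed before unblinding, but it does not threaten the trial's main conclusions.

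**What to change.** **(a) Settle the reach.** Add to SAP 7.11.1 a sentence such as: *AEs flagged as continued solicited AEs that are serious, are medically attended, or lead to withdrawal of IP or discontinuation of the trial are included in all SAE, MAAE and discontinuation summaries and in Table 7.d.*

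**(b) Settle the 28-day endpoint**, by one of two routes:
- Report the percentage with any unsolicited AE including the flagged events, as the protocol classifies them, and add one supplementary table without them.
- If the sponsor prefers to exclude them from the 28-day tables by system organ class and preferred term, limit the exclusion to those tables and declare it in SAP 7.13 as a change from protocol 10.1.2 and 10.4.2.

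Whichever route is taken, the text should also say how recurring solicited AEs are handled, so that continuing and recurring events follow a stated rule.

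**Cost.** SAP wording and, under the first route, one extra table. The flag is already on the AE CRF, so no new data are needed. The downside of inclusion is that some episodes appear under both the solicited and unsolicited headings; a footnote can say so.

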7.11.2 Clinical Laboratory Evaluations

Not applicable.

7.11.3 Vital Signs

The vital signs collected in the trial include systolic and diastolic blood pressure, heart rate, body temperature, height, weight, and body mass index (BMI). Summary statistics (number of subjects [n], mean, SD, median, minimum, and maximum) will be presented by trial group and visit (observed data and changes from Baseline).

7.11.4 12-Lead ECGs

Not applicable.

7.11.5 Other Observations Related to Safety

Not applicable.

7.12 Interim Analysis

No interim analysis is planned for this trial.

7.13 Changes in the Statistical Analysis Plan

The SAP contains no changes to the planned analyses described in the protocol.

Appendix A Schedule of Trial Procedures

Table 8.a Schedule of Trial Procedures

Visit number	V1	V2	V3	V4	V5 ^(a)
	Day 1	Day 30	Day 90	Day 120 (V3+30 days)	Day 270 (V3+180 days)
Day	M0	M1	M3	M4	M9 (ET)
Visit window (days)	±0	-1/+7	-4/+7	-1/+7	-7/+14
Informed consent/assent ^(b)	X				
Assessment of eligibility criteria ^(c)	X				
Demographics	X				
Medical history	X				
Concomitant medications/vaccinations ^(d)	X	X	X	X	X
Check criteria for delay of trial vaccination	X		X		
Check contraindications to trial vaccination			X		
Complete physical examination ^(e)	X		X		
Targeted physical examination ^(f)		X		X	X
Vital signs ^(g)	X	X	X	X	X
Pregnancy test ^(h)	X		X		
Pregnancy avoidance guidance ⁽ⁱ⁾	X	X	X	X	
Randomization	X				
Blood sample for dengue neutralizing antibodies (5 mL) ^(j)	X			X	X
Trial dose administration ^(k)	X		X		
Injection site evaluation ^(l)	X		X		
Diary card ^(m)	Distribution	X		X	
	Review/collection		X		X
Unsolicited adverse events (AE) ⁽ⁿ⁾	X	X	X	X	
Serious adverse events (SAE) and AEs leading to subject discontinuation or withdrawal ^(o)	X	X	X	X	X
Medically attended AEs (MAAE) ^(o)	X	X	X	X	X

ET=Early Termination; M=month; V=visit

(a) If the subject terminates early, Day 270 (M9) procedures should be performed.

(b) Up to 28 days prior to the day of randomization.

(c) Review of inclusion/exclusion criteria will be performed prior to administration of the first trial dose at Day 1 (M0). After eligibility is assessed and written informed consent/assent has been obtained, subjects will be randomized to receive either 2 doses of TDV or placebo by subcutaneous (SC) injection.

(d) Any other vaccination against any flavivirus (licensed or investigational, including any other dengue vaccine) during the entire trial period, all concomitant medications, vaccine history from 1 month (minimum 28 days) prior to administration of each trial dose of TDV or placebo up to 1 month (minimum 28 days) thereafter, steroids and immunostimulants within 60 days prior to Day 1 (M0), immunoglobulins and blood products within 3 months prior to Day 1 (M0), and immunosuppressive therapy within 6 months prior to Day 1 (M0).

- (e) Physical examination including measurement of vital signs (see footnote [g]), weight and height; body mass index (BMI) will be calculated automatically. Measurement of height is only required at Day 1 (M0).
- (f) Subjects may undergo a brief symptom-directed physical examination. Clinically significant changes from the Baseline examination should be recorded in the subject's source documents and electronic Case Report Form (CRF).
- (g) Vital signs including (but not limited to) the measurement of systolic blood pressure, diastolic blood pressure, heart rate, and body temperature.
- (h) Pregnancy testing (serum or urine) for females of childbearing potential. Results must be confirmed and documented as negative prior to each trial dose administration. Additional pregnancy tests may be performed during the trial if deemed necessary by the Investigator. Females of childbearing potential who are sexually active will be reminded during trial visits to adhere to acceptable contraceptive methods up to 6 weeks after the last dose of IP (Day 90 [M3]).
- (i) Females of childbearing potential who are sexually active will be provided with information on acceptable methods of contraception as part of the subject informed consent/assent process and will be asked to sign a consent form/assent form stating that they understand the requirements for avoidance of pregnancy and donation of ova. Subjects will be reminded during trial visits to adhere to acceptable contraceptive methods and not to donate ova up to 6 weeks after the last dose of IP (Day 90 [M3]).
- (j) The blood sample at Day 1 (M0) should be taken prior to administration of the first trial dose. The blood sample at Visit 4 (Day 120 [M4]) should be taken at least 28 days after the second trial dose at Day 90 (M3).
- (k) TDV (Group 1) or placebo (Group 2).
- (l) Injection site assessed by trial staff for pain, erythema, and swelling for at least 30 minutes following administration of each trial dose.
- (m) Diary cards will be distributed for the collection of 1) solicited local (injection site) AEs for 7 days following administration of each trial dose (including the day of administration), and 2) solicited systemic AEs for 14 days following administration of each trial dose (including the day of administration).
The Investigator will categorize all events by severity (mild, moderate or severe), and will assess causality to trial dose administration for solicited systemic events (related or not related).
- (n) Unsolicited AEs will be collected for 28 days following administration of each trial dose (including the day of administration) by interview. The Investigator will categorize events by severity (mild, moderate or severe) and will assess causality to trial dose administration (related or not related).
- (o) MAAEs, SAEs, and AEs leading to subject discontinuation or withdrawal will be collected for the trial duration. The Investigator will categorize all events by severity (mild, moderate or severe) and will assess causality to trial dose administration (related or not related).

